Study Protocol

Updated: April 2020

A randomized trial to assess the effect of a novel pre-consent survey comprised of nudges on critical care randomized controlled trial enrollment among surrogates of mechanically ventilated patients.

Co-Principal Investigator:

[name]
Perelman School of Medicine, Division of Pulmonary, Allergy and Critical Care
University of Pennsylvania
[name]
[name]

[contact] [contact]

Email: [contact]

Co-Principal Investigator:

[name], MSHP
Perelman School of Medicine, Division of Pulmonary, Allergy, and Critical Care
University of Pennsylvania
[name]
[name]

[contact]

Email: [contact]

Table of Contents

1.	Abstract					
2.	. Background and Introduction					
3.	Obj	jectives	5			
	3.1	Overall Objectives	5			
	3.2	Primary Outcome Variable(s)	5			
	3.3	Secondary Outcome Variable(s)	5			
4.	Des	sign	5			
5.	Rec	cruitment	5			
	5.1	Subjects	5			
	5.2	Informed Consent	6			
	5.3	Accrual	6			
	5.4	Key Inclusion Criteria	6			
	5.5	Key Exclusion Criteria	6			
	5.6	Remuneration	6			
6.	Rar	ndomization	6			
	6.1	Groups	6			
	6.2	Assignment	6			
7.	Pro	cedures	6			
8. Consent						
9.	Ana	alysis Plan	8			

10. Con	fidentiality of Subjects and Data	8
10.1	Data Management	8
10.2	Subject Confidentiality	9
10.3	Subject Privacy	9
11. Hur	nan Subjects Protection	9
11.1	Potential Risks	9
11.2	Potential Benefits	9
11.3	Risk/Benefit Assessment	9
12. Stu	dy Instruments1	0
12.1	Pre-consent Nudge Survey	0
12.2	Sham Mechanical Ventilation Trial Consent Form	1
12.3	Risk Perception Assessment	5
12.4	Surrogate Demographic Survey1	6
12.5	Patient Demographic Survey1	7
12.6	Debriefing Form	8
12.7	Script	9
13. Ref	erences	6

1. Abstract

Difficulty recruiting patients is a widely recognized barrier to successful completion of randomized controlled trials (RCTs) and a significant contributor to the cost of conducting such studies. Difficulty recruiting patients is particularly problematic for critical care trials which often rely on surrogate decision makers (SDMs) for enrollment decisions. Evidence suggests that behavioral interventions, or nudges, may offer novel approaches to increase enrollment in RCTs by reframing decisions without restricting choice. We aim to determine the effectiveness of a scalable bundle of non-monetary nudges on increasing enrollment rates in a sham RCT among critically ill patients.

2. Background and Introduction

The joint problems of under-enrollment and selective enrollment in RCTs have long plagued efforts to evaluate new and existing medical interventions¹⁻⁴. Under-enrollment occurs when too few research participants are enrolled to provide adequate statistical power to answer the study's primary research question, degrading the study's scientific value and hence, ethics⁵⁻⁷. Selective enrollment occurs when specific subgroups within the target population are enrolled in proportions greater or less than their representation in that population, limiting the generalizability of the trial's results and curtailing scientific value⁸.

Forty percent of National Cancer Institute-sponsored trials are never completed, according to an Institute of Medicine report⁹. Studies often go unfinished due to enrollment difficulties^{5,10-12}. Trials that fail to achieve target enrollment due to enrollment difficulties have been called the "ultimate inefficiency"⁹. Recruitment has been referred to as "the most difficult and challenging aspect of clinical trials¹³. Even when investigators enroll an adequate number of participants, they rarely do so on schedule^{12,14}, or in a manner that attracts the full range of available participants^{8,15}. Further, participant recruitment represents one of the most substantial costs of conducting clinical trials, requiring an average of 13 hours and \$500 per subject in cancer trials at academic medical centers¹⁶. Given the resources needed to successfully recruit patients to RCTs, and the gap between important research questions and available research funding, it is essential to find ways to enhance recruitment of patients to clinical trials¹⁷. Authorities have suggested that trialists should embed evaluations of recruitment strategies within their trials^{18,19}.

Behavioral economics is a relatively new discipline which merges psychology and economics to gain insights into how people make decisions. A key aspect of behavioral economics is the use of nudges. Nudges are behaviorally informed interventions which predictably influence behavior without limiting choices. Nudges have been proposed as a possible way to address difficulties in trial enrollment²⁰. Financial incentives are one form of a nudge. However, many nudges are non-monetary. An example of a non-monetary nudge is providing information about norms. Injunctive norms involve the perception of what behavior is acceptable, while descriptive norms highlight what behaviors others are engaging in. Individuals are more likely to participate in an activity if they perceive it as acceptable and common. The duty of reciprocity is the sense that one should repeat pro-social behavior from which they have benefited. The mere-measurement effect is also known as the self-prophecy nudge. It reflects a tendency to perform actions after being asked about the action in a hypothetical setting. The foot-in-the-door nudge involves asking a participant to complete a small request which has a high consent rate followed by a larger request.

3. Objectives

3.1 Overall Objectives

The goal of this study is to test whether a novel pre-consent survey with incorporated nudges increases the enrollment rate into a sham RCT among critically ill patients. To accomplish this goal we will assess quantitatively how many surrogates assigned to each study arm enroll a patient into the sham RCT. We will also quantitatively assess for undue and unjust inducement.

3.2 Primary Outcome Variable(s)

This randomized trial has the single primary outcome of proportion of SDMs who enroll the patient into the sham RCT.

3.3 Secondary Outcome Variable(s)

Secondary outcomes included undue inducement, unjust inducement, patient and surrogate characteristics associated with enrollment. Undue inducement was defined as an interaction between intervention and risk perception on enrollment rate. Unjust inducement was defined as an interaction between intervention and highest level of education completed on enrollment rate.

4. Design

This is a single-blinded randomized controlled among surrogates of patients requiring mechanical ventilation admitted to one of ten ICUs across two University of Pennsylvania Health System (UPHS) hospitals.

5. Recruitment

5.1 Subjects

We will be recruiting 182 surrogate decision-makers of patients requiring mechanical ventilation admitted to one of ten ICUs across two UPHS hospitals. The research coordinator will review the electronic medical record of patients admitted to the ICUs to identify eligible participants. The coordinator will contact the attending physician for any identified patient to confirm eligibility and seek approval for the study team to approach the patient's family. The coordinator will approach approved families if they are present in the patient's room at the time of recruitment. The coordinator may defer approach if there is a procedure underway or if the family is in visible distress.

The eligibility criteria for participation are as follows:

Eligibility Criteria			
ICU length of stay >24hrs			
Mechanically ventilated via an endotracheal tube			

Over 18 years of age			
Anticipated to remain using an endotracheal tube at least 24 more hours			
No limitations on life extending care			
Surrogate fluent in English			
Not enrolled in an active ICU trial			
Patient unable to consent for self			
ICU attending is not a study investigator			
ICU attending identifies the patient's family as distrustful of the medical system			
ICU attending declines approach for any reason (reason to be documented)			
Surrogate present in patient's room			

5.2 Informed Consent

A waiver of informed consent has been approved by the University of Pennsylvania Institutional Review Board. Once patients have been chart screened for eligibility, study personnel will approach potentially eligible surrogate. Study personnel will introduce themselves to the patient, inform the patient that they are part of a group conducting a research study, and ask permission to sit down and tell the patient more.

5.3 Accrual

We have received approval from the University of Pennsylvania IRB-approved protocol and obtained approval to conduct this study in all 6 ICUs located at the Hospital of the University of Pennsylvania and all 4 ICUs located at Presbyterian Hospital. Using an estimated baseline enrollment rate of 30% in the control group, a total of 182 participants achieves at least 80% power to detect a 20% absolute difference at alpha of 0.05. We will consecutively recruit all eligible surrogates from the ICU until we reach our target sample size. We will attempt visit each ICU session at least once a day. The research coordinator will approach eligible surrogates while they are present in the patient's room. For surrogates who initially defer a decision we will attempt to reengage the following day and each subsequent recruiting day until we either have a definitive decision or until the patient is ineligible. We anticipate that we can recruit at least 4 patients per week.

5.4 Key Inclusion Criteria

The eligibility criteria, all of which must be met, are:

- 1. Patient and surrogate must be 18 or older
- 2. ICU length of stay > 24 hours
- 3. Mechanically ventilated via an oral endotracheal tube
- 4. Patient is unable to consent for themselves

5.5 Key Exclusion Criteria

Patients will be excluded if one of the following criteria is met:

- 1. Limitations on life extending care
- 2. Anticipated extubation or tracheostomy placement in next 24 hours
- 3. Enrolled in another ICU trial
- 4. ICU attending is a study investigator

Surrogates will be excluded if one of the following criteria are met:

- 1. Not fluent in English
- 2. Identified by the ICU attending as having mistrust in the healthcare system

3. Not present in the patient's room at the time of recruitment

5.6 Remuneration

Subjects will not receive any compensation for participation.

6. Randomization

6.1 Groups

Surrogates who indicate they are willing to hear about a research study will be randomized to receive either a pre-consent nudge survey or standard informed consent procedures. The two groups only differ in the initial approach, whether they are asked to complete a survey before being informed of the sham trial or whether they are invited to consider the sham trial without a pre-consent survey. Both groups then fill out identical risk assessments and demographic surveys. After indicating their sham trial enrollment decision and completing risk assessments and demographic surveys, surrogates will be debriefed (see debriefing script).

6.2 Assignment

Group allocation will be determined by the REDCap randomization module with assignment probabilities of 50% to each group stratified by research coordinator.

7. Procedures

Study procedures are as following:

- 1. The research coordinator will review the electronic medical record of patients admitted to each of 10 ICUs to determine eligibility and documenting the results in the study screening database.
- 2. The research coordinator will contact the ICU attending of patients screened as eligible to confirm eligibility.
- 3. The research coordinator will visit each eligible patient's room to assess for the presence of visitors.
- 4. If visitors are present the research coordinator will enter patient information into the REDCap study module on the screening tablet.
- 5. The research coordinator will enter the room, identify themselves and confirm that the visitor is the patient's surrogate decision maker.
- 6. The research coordinator will ask the patient's identified surrogate decision maker if they are willing to hear about a research study.
- 7. Surrogate decision makers who indicate their wiliness to hear about a research study will then be randomized in the REDCap randomization module (as above).
- 8. If the participant is randomized to the intervention arm the research coordinator will follow the script (see below) introducing the survey. Following completion of the survey the research coordinator will then ask if they are willing to hear about a research trial.
- 9. If the participant is randomized to the control arm the research coordinator will follow the script (see below) introducing the sham mechanical ventilation weaning trial.

- 10. After the surrogate makes an enrollment decision (regardless of the decision) for the sham mechanical ventilation trial they will be asked to complete the risk perception assessment and demographic surveys.
- 11. If the surrogate askes for more time to make an enrollment decision the research coordinator will ask for a good time to return for a decision. Risk perception assessment and demographic survey data will be deferred until after a decision is made. The research coordinator will follow up the following day (or time set by surrogate) to seek an enrollment decision. Repeated attempts to obtain an enrollment decision will continue each recruitment day until a decision is made or until eligibility criteria is no longer met.
- 12. Immediately following the sham trial enrollment decision, risk assessment and demographic surveys the research coordinator will debrief the surrogate (see script below).
- 13. The research coordinator will update the screening database with the results of the recruitment attempt.
- 14. The research coordinator will document additional clinical data from the electronic medical record for participating patients into the REDCap study database.
- 15. We will continue subject recruitment until target enrollment is reached.

8. Consent

A waiver of informed consent has been approved by the University of Pennsylvania Institutional Review Board. Once patients have been chart screened for eligibility, study personnel will approach potentially eligible surrogate. Study personnel will introduce themselves to the patient, inform the patient that they are part of a group conducting a research study, and ask permission to sit down and tell the patient more. Following the study procedures and debriefing the participant will retain the debriefing handout which includes instructions on how to withdrawal from the study.

9. Analysis Plan

As we do not have any strong a priori evidence that any of the collected demographic will be strongly associated with the primary outcome, we will perform an unadjusted analysis as the primary analysis. The primary outcome will be an intention-to-treat analysis of the proportion of participants who enroll in the sham clinical trial. The intervention arm will be compared to the control arm using a chi-square test. In secondary analyses, we will test for undue inducement by assessing the interaction between the study group and risk perception on enrollment rate. We will test for unjust inducement by assessing the interaction between study group and level of education on enrollment rate. Stata v14 will be used for all analyses. Unless otherwise specified, a p-value <0.05 will be considered significant.

We will conduct a post-hoc exploratory analysis of patient and surrogate variables associated with sham trial enrollment. We will have a third party with critical care trial recruitment expertise, blinded to the data, review and rank the variables based on their mechanistic plausibility to impact enrollment decisions. The number of included variables in the final model will be determined by the number of events (enrollments into the sham trial) to not exceed a 1:10 covariate to event ratio.

10. Confidentiality of Subjects and Data

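### Allocation is stratified by research coordinator, but the primary chi-square test ignores that factor: valid, but it gives up power if coordinators differ

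*Combined protocol and SAP*

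**What the plan says.** - **Allocation (Section 6.2).** REDCap assigns the arms with "assignment probabilities of 50% to each group stratified by research coordinator". Blocking and the number of coordinators are not stated.
- **Primary analysis (Section 9).** The plan says "we will perform an unadjusted analysis as the primary analysis", and then: "The intervention arm will be compared to the control arm using a chi-square test".
- **Reason for not adjusting (Section 9).** "we do not have any strong a priori evidence that any of the collected demographic will be strongly associated with the primary outcome". The research coordinator is not mentioned.
- **Sample size (Section 5.3).** The assumed control rate is 30%. On that basis the plan states: "a total of 182 participants achieves at least 80% power to detect a 20% absolute difference at alpha of 0.05".
- **Role of the coordinator (Sections 5.1 and 7).** "The coordinator may defer approach if there is a procedure underway or if the family is in visible distress". In the control arm, "the research coordinator will follow the script (see below) introducing the sham mechanical ventilation weaning trial"; the intervention arm is scripted too. When a surrogate wants more time, the coordinator returns on later days for the decision.

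No analysis, primary or sensitivity, takes the coordinator into account.

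**The concern.** The coordinator is the one variable the design chose to balance on, and the primary test leaves it out. The stated reason does not cover the omission, because the coordinator is not a collected demographic.

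The coordinator could plausibly affect the outcome, which is a surrogate's decision after a personal approach. The coordinator decides when to approach, presents the sham trial and follows up for an answer. Scripts in both arms may narrow such differences without removing them.

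If coordinators differ clearly in enrollment success, variation between them stays in the error term of the unstratified test, and a stratified test on the same 182 surrogates has more power. If they differ little, almost nothing is at stake. Settling the point in advance also fixes which result counts should stratified and unstratified p-values fall on either side of 0.05.

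**Working it through.** **1. The plan's own figure.** Inputs from Section 5.3: 30% versus 50%, alpha 0.05 (taken as two-sided), 80% power, 1:1.

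- Unpooled variance: n per arm = (1.960 + 0.842)² × (0.30×0.70 + 0.50×0.50) / 0.20² = 90.3, so 91 per arm and 182 in total. This matches the plan.
- Power at 91 per arm, unpooled: Φ(0.20/√(0.46/91) − 1.96) = 80.3%.
- Power at 91 per arm, pooled: Φ((0.20 − 1.96×√(2×0.24/91)) / √(0.46/91)) = 79.1%.

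The target therefore sits at 80% with almost no slack.

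**2. Why stratifying can help (large-sample check).** Take two equal coordinators with control rates of 10% and 50%, and 20 points added in each.

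- Averaged over coordinators, the within-coordinator variance is 0.17 (control) + 0.21 (intervention) = 0.38, against 0.46 overall.
- The null term uses mid-rates of 20% and 60%: (0.16 + 0.24)/2 = 0.20, against 0.24 overall.
- Stratified power = Φ((0.20 − 1.96×√(2×0.20/91)) / √(0.38/91)) = Φ(1.08) = 86.1%.
- At 20% and 40% the two variances are 0.44 and 0.23, which gives Φ(0.87) = 80.8%.

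**3. Why the chi-square test can be conservative.** With blocked allocation, its variance estimate includes between-coordinator variation that blocking has removed. At 10% and 50% in both arms, the true-to-assumed variance ratio is 0.17/0.21 = 0.81. Actual size is then 2×(1 − Φ(1.96/√0.81)), about 2.9%.

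**4. Simulation.** There were 200,000 trials per scenario, N = 182, caseloads as equal as possible, and 20 points added in every stratum. Pearson chi-square and CMH were both run without continuity correction. Allocation within coordinator was either permuted blocks of 4 or simple 50:50. The number of coordinators, caseloads, control rates and block size are assumptions.

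| Control rates by coordinator | Blocked: power, chi-square / CMH | Blocked: chi-square type I error | Simple: power, chi-square / CMH |
|---|---|---|---|
| 25, 35% | 79.2 / 79.4 | 4.9% | 79.1 / 79.1 |
| 20, 40% | 79.7 / 81.0 | 4.4% | 79.3 / 80.7 |
| 10, 50% | 81.6 / 86.5 | 3.0% | 79.1 / 86.1 |
| 20, 30, 40% | 79.6 / 80.4 | 4.6% | 79.1 / 79.7 |
| 10, 30, 50% | 80.6 / 84.0 | 3.6% | 79.1 / 83.4 |
| six over 20–40% | 79.4 / 80.0 | 4.9% | 79.1 / 78.7 |

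CMH type I error is 4.9 to 5.1% with blocking. Under simple allocation, chi-square type I error is 5.0 to 5.2% throughout. The simulated powers agree with the formulas in step 2. With two or three coordinators that differ, the gain hardly depends on blocking; the conservative error rate does.

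**5. Power cost of CMH when coordinators do not differ (points).**

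| Coordinators | Blocked | Simple |
|---|---|---|
| Two | 0.2 | 0.4 |
| Six equal (30 or 31 each, so none pooled) | 0.1 | 1.3 |
| Ten equal, no pooling | 0.2 | 2.1 |
| Ten equal, those under 30 pooled | 0.1 | 0.1 |
| Six of 30 plus one of 2, those under 30 pooled | 0.3 | 1.5 |

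**The case against.** The strongest reply is that nothing breaks. The plan openly chooses an unadjusted analysis, and its sample size was calculated for that same comparison. In every scenario tried, chi-square power stays at about 79% or above. This stands, and it is why the point is one of efficiency only.

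Second, the gain is assumed. Gains of 3 points or more need control rates running from 10% to 50% among staff who follow the same script, and nothing in the documents points to such a spread. At moderate spreads the gain is about 1.5 points or less, and with six coordinators under simple allocation CMH loses about 0.4 points. This also stands.

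Third, deferring an approach happens before randomization, so it cannot differ by arm. That is correct. It can still give coordinators different case mixes, which is enough to make the coordinator prognostic.

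Fourth, pooling small strata can cancel the benefit. With ten equal coordinators (18 or 19 surrogates each), all fall below 30 and CMH becomes essentially the chi-square test. With rates spread over 10–50% and blocking, power is 80.2 for chi-square, 82.1 for unpooled CMH and 80.1 for pooled CMH. The gain is lost, but the result is no worse than the current plan. The cutoff of 30 is a judgment, not a figure from the documents.

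These replies limit the size of the point. None explains why the stratification factor is left out.

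**Conclusion.** The concern holds as a minor, optional improvement. The primary test does not use the factor by which the trial randomizes, and the stated reason does not cover that factor. The chi-square test remains valid: it holds about 5% under simple allocation, and falls below 5% only if allocation is blocked within coordinator and coordinators differ.

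The power forgone ranges from nothing to about 1.4 points at modest differences between two coordinators, 3.4 to 4.3 points for three coordinators at 10, 30 and 50%, and 5 to 7 points for two at 10 and 50%. The documents cannot say where in this range the trial lies. Confidence in the mechanism is high; confidence that the gain is material is moderate at most.

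**What to change.** **Section 9.** Make the primary test a CMH test stratified by research coordinator, report the Mantel-Haenszel risk difference with its 95% confidence interval, and keep the unstratified chi-square test as a sensitivity analysis. State a pooling rule based on total counts and applied before data are seen by arm: coordinators with fewer than 30 randomized surrogates form one combined stratum.

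**Section 6.2.** State whether allocation is blocked within coordinator.

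**Cost.** Two sentences in Section 9 and one in Section 6.2. No new data are needed, because the coordinator is already recorded as the randomization stratum. The power cost if coordinators do not differ is shown in step 5: at worst about 1.5 points with pooling, in the cases tried. Pooling also gives up part of the gain: with caseloads of 60/50/40/12/10/10, control rates of 10/30/50% repeated and blocking, the gain is 2.4 points instead of 3.0.

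If the investigators prefer to keep the chi-square test as primary, the least that is needed is a sentence saying why the stratification factor is omitted, with the coordinator-stratified test as a sensitivity analysis.

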12.4 Surrogate Demographic Survey

□ Separated

Penn Medicine	Study ID
Demographic and Clinical information:	
Please answer the following to the best of your ability about yourself (all will be kept confidential and secure and will not be shared):	
1. Are you officially designated as the patient's durable power of attorney for health care? ☐ Yes ☐ No	8. Please specify your ethnicity: Hispanic or Latino Not Hispanic or Latino
2. Have you ever had a life-threatening illness or injury for which you needed life support to keep yourself alive? This type of care would usually mean that you were in an ICU, and being treated with a breathing machine or other machines or medicines necessary to keep you alive.	9. Please specify your race: American Indian or Alaskan Native Asian Native Hawaiian or Other Pacific Islander Black or African-American White or Caucasian Other
Yes □ No 3. Have you ever participated in a medical research trial? This would usually mean being asked for consent before taking an experimental medication or other intervention and being monitored for a response. Yes □ No	10. What is your highest level of completed education? Less than High School High School/GED Some College College Degree Post-College Degree (MA, Professional
4. Has anyone you known ever participated in a medical research trial? This would usually mean being asked for consent before taking an experimental medication or other intervention and being monitored for a response.	degree, PhD) 11. What is your relationship to the patient? □ Spouse
☐ Yes ☐ No 5. What is your gender? ☐ Male ☐ Female	☐ Adult child ☐ Parent ☐ Sibling ☐ Other blood relative ☐ Friend
6. What is your age? 7. What is the your marital status?	□ Other
☐ Widowed ☐ Married/Partnered ☐ Never married ☐ Divorced	

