12.5 Patient Demographic Survey

Penn Medicine	Study ID
Please answer the following to the best of your ability about your loved one (all will be kept confidential and secure and will not be shared):	
1. In the past 3 months, approximately how long has the patient spent in a hospital or other health care facility?	5. What is the patient's gender?
☐ Less than 1 week	□ Male
☐ 1 week to 1 month	☐ Female
□ 1 month to 3 months	_
☐_Entire 3 month	6. What is the patient's age?
	7. What is the patient's marital status?
2. Before the patient's current Intensive Care (ICU) stay, have they ever had a life-threatening illness or injury for which they needed life support to keep them alive? This type of care would usually mean that they were in an ICU, and being treated with a breathing machine or other machines or medicines	 Widowed Married/Partnered Never married Divorced Separated
necessary to keep them alive.	8. Please specify the patient's ethnicity:
☐ Yes ☐ No ☐ I don't know 3. Has the patient ever participated in a medical	☐ Hispanic or Latino ☐ Not Hispanic or Latino
research trial? This would usually mean being asked	9. Please specify the patient's race:
for consent before taking an experimental	☐ American Indian or Alaskan Native
medication or other intervention and being	☐ Asian
monitored for a response.	 Native Hawaiian or Other Pacific Islander
☐ Yes ☐ No ☐ I don't know	☐ Black or African-American
4. Based on the information that has been shared	 □ White or Caucasian □ Other
with you about your loved one's condition, do you	
feel that he or she is:	10. What is the highest level of education the patient has completed?
□ Stable	□ Less than High School
 Improving Worsening 	☐ High School/GED
- And Sering	 ☐ Some College ☐ College Degree
	☐ Post-College Degree (MA, Professional

degree, PhD)

13. References

- 2. Ellenberg SS. Randomization designs in comparative clinical trials. The New England journal of medicine 1984;310:1404-8.
- 4. Altman DG. Statistics and ethics in medical research: III How large a sample? British medical journal 1980;281:1336-8.

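### Does the 1:10 limit on the exploratory enrollment model need to say that it counts model terms rather than survey items?

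*Combined protocol and SAP*

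**What the plan says.** Section 9 (Analysis Plan) describes the model in its last paragraph: "We will conduct a post-hoc exploratory analysis of patient and surrogate variables associated with sham trial enrollment". A third party who is blinded to the data ranks the candidate variables by how plausibly they could affect the decision. The size rule is then a single sentence. It begins "The number of included variables in the final model will be determined by the number of events (enrollments into the sham trial" and ends with the limit, "to not exceed a 1:10 covariate to event ratio". The first half counts variables and the second half counts covariates. Neither word is defined, and no coding or collapsing of answer categories is given.

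The candidates include the surrogate form (section 12.4) and the patient form (section 12.5). Several items have many options: "What is your relationship to the patient" has seven, each race item has six, and "What is the highest level of education the patient has completed" has five, as does the matching surrogate item.

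Section 3.3 names "patient and surrogate characteristics associated with enrollment" among the secondary outcomes. The exploratory model is the only analysis described for it.

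**The concern.** A binary item costs one parameter in a regression model, but a seven-option item entered as categories costs six. If each item counts as one toward the limit, a model can hold the permitted number of items and still estimate several times as many coefficients. The 1:10 ratio is the only stated control on the model's size, so on that reading it would control little. The consequences would be categories with no enrollments or no refusals, fits that fail, and wide intervals for the characteristics that section 3.3 promises to report. With no coding fixed, categories could also be merged after outcomes are known, which would weaken the blinded ranking.

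**Working it through.** **Inputs.** Section 5.3: 182 surrogates, control enrollment 30%, absolute difference 20 points (so 50% with the survey), 80% power, alpha 0.05. Section 6.2: equal allocation, so 91 per arm. Sections 12.4 and 12.5: answer options. Assumptions: two-sided alpha, no losses, a logistic-type model for enrollment.

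**1. The plan's own figure.** With unpooled variance, n per arm = (1.960 + 0.842)² × (0.30 × 0.70 + 0.50 × 0.50) / 0.20² = 90.3. This rounds up to 91 per arm, or 182 in total, so the stated size reproduces.

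**2. Expected events and the ceiling.**
- At 30% and 50%: 91 × 0.30 + 91 × 0.50 = 72.8 enrollments. One tenth, rounded down, is 7.
- At 30% in both arms: 182 × 0.30 = 54.6 enrollments. The ceiling is 5.

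In both cases the enrolled are the smaller outcome group (72.8 v 109.2, and 54.6 v 127.4), so counting enrollments is the right basis at the planned rates.

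**3. Parameters per item** (options minus one; age counted as one).
- Surrogate form, 11 items: relationship 6, race 5, education 4, marital status 4, and seven items at 1. Total 26.
- Patient form, 10 items: race 5, education 4, marital status 4, recent time in hospital 3, three items with three options at 2 each, and three items at 1. Total 25.
- Together: 21 items and 51 parameters. Eleven items cost more than one parameter and ten cost exactly one.

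**4. Seven items at 72.8 enrollments, every category entered.**

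| Items in the model | Parameters | Enrollments per parameter |
|---|---|---|
| Seven one-parameter items, or any seven collapsed to one term each | 7 | 10.4 |
| Education + six one-parameter items | 10 | 7.3 |
| Education, relationship + five | 15 | 4.9 |
| Education, relationship, race + four | 19 | 3.8 |
| The seven largest items (6+5+5+4+4+4+4) | 32 | 2.3 |

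With five items at 54.6 enrollments, the largest case is 6+5+5+4+4 = 24 parameters, again 2.3 per parameter.

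**5. The two readings of the limit.**
- A covariate is a model term: 7 terms on 72.8 events is 10.4 events per term. The rule already does what a clarification would ask of it.
- A covariate is a survey item: 7 items on 72.8 events satisfies the stated ratio. The lower figures in step 4 are measured against events per parameter, a standard the plan did not set.

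**6. Reach.** Section 9 compares the arms by an unadjusted chi-square test and tests undue and unjust inducement by separate interactions of arm with risk perception and with education. None of these takes a term from the exploratory model.

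**The case for a change.** The strongest case for a change is that the sponsor chose to state a size limit, so the limit should bind, and one sentence would make it do so. The multi-option items are likely choices: education is already important enough to define unjust inducement. Sparse categories are also a real possibility. The documents give no category shares, so take shares s of 6%, 4% and 2% as assumptions. At 40% pooled enrollment, the chance that a category has no enrollments or no refusals is (1 − 0.4s)^182 + (1 − 0.6s)^182 − (1 − s)^182, which gives 1.3%, 6.5% and 31.8%.

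Part of this stands. The unit is undefined, the coding is open, and a large model with rare categories can fail to fit. Merging categories after seeing outcomes would be a weakness, though a limited one in an analysis reported as exploratory.

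The rest does not carry far. A 2% category is about 4 of 182 people (182 × 0.02 = 3.6), and an analyst would normally merge it before fitting. An empty cell also shows itself in the output. The 32-parameter model requires relationship plus both race, both education and both marital-status items, all uncollapsed, to rank highest. The blinded expert picks by plausibility, from a pool that also includes chart data (section 7, step 14) and possibly the risk rating (section 12.3), so no average over random sets of items describes the likely model. Failure rates from simulated fits depend heavily on the category shares assumed, so they cannot size the problem. No loss of precision has been shown for any section 3.3 characteristic. Basing the limit on the smaller outcome group would matter only if pooled enrollment exceeded 50%; the design implies 40%.

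**Conclusion.** No change is needed. This is missing detail of a kind that analysts fill sensibly, in a model whose results can only suggest hypotheses. At the planned rates the ceiling is 7. Depending on how items are coded, seven items from the two demographic forms use between 7 and 32 parameters, or 10.4 to 2.3 enrollments per parameter. The low end needs both the item-counting reading and full category entry for the largest items; ordinary practice is to count terms or collapse categories. On either reading the stated ratio is met.

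The conclusion rests on the design rates holding roughly, on the analysis being presented as exploratory, and on the primary and inducement analyses staying separate from this model, as section 9 describes. The figure of 32 covers the two demographic forms only, because the chart variables are not listed. Noting in the eventual report how categories were coded, and whether that was settled before outcomes were seen, would answer what remains.
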